Test Up Now Education Program

NCT04304001

Document Date: 1/26/2022

Study Protocol and Statistical Analysis

Study Protocol

The TUNE-UP study is designed as a two-group pretest/posttest pragmatic randomized controlled trial. The study uses the parallel group, two arm superiority trial design with 1:1 allocation ratio. The pragmatic trial aims to test the effectiveness of the intervention in the setting of community health centers. To conduct the intervention trial, 115 participants were randomized at the time of enrollment following completion of the baseline survey. The two experimental arms are: 1) an intervention group which receives the adapted Screen to Save (S2S) educational materials, a tailored brochure for African Americans on colorectal cancer (CRC) screening with input from focus group research, and CHA in-person and cellphone education and counseling supplemented by text messages; and 2) a control group which receives the brochure only. Participants in both study arms received communication from their CHC to receive their stool-based testing kit. The primary outcome is CRC screening by 12-months post-intervention (i.e., receipt of the stool-based test). The intermediary CRC screening outcome is measured at 3-months. Secondary outcomes included CRC knowledge and CRC screening self-efficacy.

Study participants and setting

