All statistical analyses were performed using SAS 9.4. First, summary statistics were generated for all variables. Then bivariate analyses were conducted for key variables to compare differences between the intervention and control arms. Proportions calculated from categorical variables were compared using a chi-square test; means obtained continuous variables were compared using two-sample t-test. The multivariate analyses were conducted using the GEE procedure in SAS that implements the generalized estimating equations regression. Analyses were performed using an intent-to-treat approach that includes all participants randomized. Significance tests were two-sided and employed an overall significance level of $\alpha=0.05$. For each arm, the proportion of participants who receive CRC screening by 12 months was computed. The chi-square test was used to compare the two treatment arms for screening receipt. If the proportion of participants receiving CRC screening in the intervention arm is at least 15% higher than that in the control arm, the intervention will be determined to be effective. In addition, since our sample size gets small when participants are stratified by community health center or sex, we will use Fisher's exact test to assess the effect of the intervention. To assess the influence of key covariates (age, income, marital status, education, insurance status) on the primary outcome, logistic regression analysis was employed. In addition, to investigate treatment effects over time (baseline, 3 months, and 12 months), we will estimate hazard ratios by fitting Cox proportional models using time-varying covariates. In these models, the receipt of CRC screening will be regressed at each actual time point on time elapsed since baseline to test for an interaction between time and treatment group. The basic model will be repeated, adjusting for age, income, marital status, education, and any other significant covariates at baseline. To test the proportional hazard assumption, the Kaplan-Meier curve and the Schoenfeld residuals will be used for fixed and time-varying covariates, respectively.

Mediation and moderation analyses will be conducted to determine why and when variables are related, respectively. We will focus on specific mediators to include CRC perceived susceptibility, CRC self-efficacy, and CRC knowledge in the conceptual model.

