Additionally, we will assess the moderator variables (i.e., sex, health literacy, family history of cancer) to determine under what condition (i.e., when) a given predictor X/independent variable (IV) is related to an outcome Y/dependent variable (DV). We will assess whether the moderation effect is enhancing (i.e., that is, increasing the moderator would increase the effect of the predictor on the outcome), buffering (i.e., that is, increasing the moderator would decrease the effect of the predictor on the outcome), or antagonistic (i.e., where increasing the moderator would reverse the effect of the predictor on the outcome). We will apply hierarchical multiple regression to examine the effects of the moderating variable. We will assess the interaction effect between X and M and whether or not such an effect significantly predicts the occurrence of Y. All variables will be standardized to facilitate data interpretation and avoid multicollinearity. We will fit a regression model predicting the outcome from both the predictor and moderator variables. We will check that both the effect of the predictor and the effect of the moderator, as well as the model (R²) are statistically significant. Then, we will fit another regression model that includes the interaction effect of the first model and check for a statistically significant R² change and a statistically significant effect of the interaction term to determine if moderation is occurring (i.e., both are statistically significant).

Mediation analysis allows assessment of each covariate's impact on the primary outcome independent of whether the intervention's effect is significant; thus, adding to scientific understanding of the relevance of each. To examine the mediating effects on the primary outcome of each of the short items scored on a Likert-type scale, we will follow the strategy of Baron and Kenny. We will conclude that the candidate covariate is indeed a mediator of the effects of the intervention if: (1) the treatment group indicator is significant; and (2) the candidate covariate is significant, and the coefficient estimate of the treatment group indicator is smaller in absolute value than its counterpart in analysis.

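### The only success rule is an observed gain of at least 15%, with no link to the two-sided 0.05 test and no statement of whether 15% is absolute or relative

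*Combined protocol and SAP*

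**What the plan says.** The Study Protocol section describes a superiority trial with 115 participants randomised: "The study uses the parallel group, two arm superiority trial design with 1:1 allocation ratio". The primary outcome is colorectal cancer screening by 12 months.

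The first paragraph of the Statistical analysis section sets the inferential frame: "Significance tests were two-sided and employed an overall significance level of" 0.05. For each arm "the proportion of participants who receive CRC screening by 12 months was computed", and "The chi-square test was used to compare the two treatment arms for screening receipt". The next sentence is the decision rule: "If the proportion of participants receiving CRC screening in the intervention arm is at least 15% higher than that in the control arm", then "the intervention will be determined to be effective".

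No other sentence gives a criterion for effectiveness. Later in the same section, joint significance conditions are written out for the secondary questions. For moderation, two results are checked "to determine if moderation is occurring (i.e., both are statistically significant"). For mediation, the conditions begin "1) the treatment group indicator is significant; and (2) the candidate covariate is significant".

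**The concern.** As written, the threshold is sufficient for success. It applies to the observed proportions and takes no account of sampling error, although a test with a stated error rate has just been specified for the same comparison. The plan does not say which of the two governs.

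The threshold is also undefined. At a control rate of 30%, a gain of 15 percentage points means 45%, while a gain of 15% in relative terms means 34.5% (0.30 × 1.15). These are very different hurdles.

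What is at stake is the primary conclusion. One 12-month result could be reported as effective under the rule and non-significant under the test. Parts of the document are in the past tense, so the choice of criterion and of scale could be made once results are known.

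**Working it through.** **Inputs.** From the documents: 115 randomised 1:1, all analysed as randomised, binary 12-month outcome, chi-square test, two-sided 0.05. Assumed, because the documents do not give them: arm sizes (58 intervention/57 control, and the reverse), control rates (shown as ranges), and no continuity correction. The plan states no power or control rate, so there is no figure of its own to reproduce.

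**Formulas.** For a/n1 in the intervention arm against c/n0 in control, with b = n1 − a, d = n0 − c and N = n1 + n0:

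- chi-square = N(ad − bc)² / [n1 · n0 · (a + c) · (b + d)], significant above 3.84
- 95% CI = difference ± 1.96 × √[p1(1 − p1)/n1 + p0(1 − p0)/n0]

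**Rule met, test not significant.** 26/58 (44.8%) against 17/57 (29.8%) is +15.0 points.

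- ad − bc = 26×40 − 32×17 = 496
- Chi-square = 115 × 496² / (58 × 57 × 43 × 72) = 2.76, p = 0.096
- Standard error 0.0891, 95% CI -2.5 to +32.5 points

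At the same control count, significance first appears at 28/58, which is +18.5 points (chi-square 4.11, p = 0.043).

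**Test significant, gain under 15 points.** 52/58 (89.7%) against 43/57 (75.4%) is +14.2 points.

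- ad − bc = 52×14 − 6×43 = 470
- Chi-square = 115 × 470² / (58 × 57 × 95 × 20) = 4.04, p = 0.044
- Standard error 0.0696, 95% CI +0.6 to +27.9 points

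**Ratio reading met, test far from significant.** 20/58 (34.5%) against 17/57 (29.8%) is a ratio of 1.16 and +4.7 points.

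- ad − bc = 20×40 − 38×17 = 154
- Chi-square = 115 × 154² / (58 × 57 × 37 × 78) = 0.29, p = 0.59

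**Where the conflicts lie (percentage-point reading).** For each control count I found the smallest attainable gap of at least 15 points and tested it.

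| Arms | Smallest gap ≥ 15 points is non-significant | A gap < 15 points can be significant |
|---|---|---|
| 58/57 | control 9-37 of 57 (15.8-64.9%) | control 0-5 or 43-53 of 57 (≤ 8.8% or 75.4-93.0%) |
| 57/58 | control 11-40 of 58 (19.0-69.0%) | control 0-6 or 45-54 of 58 (≤ 10.3% or 77.6-93.1%) |

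Within the ranges in the middle column, significance needs 16.9 to 20.0 points.

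**How often.** I summed exact binomial probabilities over every pair of outcomes, for both allocations.

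| True effect | Event | Control rate | Probability |
|---|---|---|---|
| None | Gain ≥ 15 points | 30-60% | 3.6-5.1% |
| None | Gain ≥ 15 points | 20% | 2.1-2.6% |
| None | Gain ≥ 15 points | 15% | 1.2-1.5% |
| None | Test significant in favour | 30-60% | 2.5-2.8% |
| None | Ratio ≥ 1.15 | 20-50% | 23-36% |
| +15 points | Gain ≥ 15 points but not significant | 20-60% | 5-13% |
| +15 points | Significant but gain < 15 points | 10% | 5-8.5% |
| +15 points | Significant but gain < 15 points | 5% or 80% | 18-23% |
| None | Both conditions met | 5-80% | at most 2.8% |
| +15 points | Both conditions met | 20-60% | 36-44% |

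**The case against.** The strongest reply is that the test and its significance level come directly before the rule, in a declared superiority trial, and that the mediation text refers to whether the intervention's effect is significant. The authors may therefore have meant both conditions to apply. That is plausible, but it is not written. The same section spells out joint conditions for mediation and moderation, and the joint reading still leaves the scale of 15% open.

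Five narrower points have some force:

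- **The reverse conflict.** The rule says if, not only if. A significant gain under 15 points fails it only on the stricter reading, and the case arises only at control rates of about 10% or less, or about 75% or more. What remains is that such a result meets no stated success criterion.
- **The absolute reading does limited harm.** The null rate peaks at about 5.1%, and at 15% control the rule is stricter than the test. The large inflation belongs to the ratio reading alone. The wording does not exclude that reading.
- **The worked example is the extreme one.** 26/58 against 17/57 has the largest p-value among the smallest-gap tables for 58/57. The others in the range go down to 0.051, so most results of about 15 points lie near the significance boundary.
- **Arm sizes and test version are assumed.** Stratified blocks of random size could leave a larger imbalance than 58/57. With a Yates correction, the tables that meet the rule without significance rise from 38 to 73, and the significant tables under 15 points fall from 32 to 14. Both kinds of conflict persist.
- **The 36-44% figure** for meeting both conditions mainly reflects sample size and is not evidence against the rule.

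**Conclusion.** The concern holds. The written rule makes an observed gain sufficient for success without a significant test, and it leaves the scale of that gain undefined. This is an error in the rule as it stands, because following it literally can declare effectiveness at p = 0.096, or at p = 0.59 on the ratio reading.

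The size depends on the reading. In percentage points, the null rate of success is at most about twice the test's favourable tail. As a ratio, roughly a quarter to a third of trials of an ineffective intervention would be called successes at control rates of 20-50%. The figures assume arms of 58 and 57, an uncorrected chi-square and the control rates shown. The gap in the text depends on none of these. It should be closed before any claim of effectiveness is made.

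**What to change.** Replace the decision sentence with wording such as:

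> Effectiveness will be concluded only if the two-sided chi-square test of the 12-month screening proportions is significant at 0.05 in favour of the intervention. The difference in proportions and its 95% CI will be reported.

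Then add one of:

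- **(a)** A difference of 15 percentage points is a benchmark of practical importance and plays no part in the decision.
- **(b)** In addition, the observed difference must be at least 15 percentage points.

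The sponsor should choose between them and say whether the chi-square is continuity-corrected, since borderline results turn on it. The change should be dated, with a statement of whether outcome data had been seen. If the analysis is already complete, report both the test and the threshold result, and do not claim effectiveness from the threshold alone.

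The cost is two or three sentences in an amendment. Under either version, an observed gain between 15 and about 17-20 points would no longer count as effective on its own at most mid-range control rates. Version (a) would also accept a significant gain under 15 points, mainly at control rates of about 10% or less, or 75% or more. Version (b) would not.

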All participants received the tailored educational brochure at the initial visit when they completed the baseline survey with the Project Coordinator. The participants who were randomized to the intervention group viewed the S2S video, and the CHA explained the contents if there were questions. This was followed by two weeks of short CHA follow-up calls, concluding with three weeks of motivational text messages on CRC screening. Participants who were randomized to the control group received the educational brochure only. Both intervention and control groups received the FIT from their CHC either in the mail, in person, or during a scheduled patient visit. The CHCs were blinded to study arm.

Community health advisor and educational materials

One CHA was trained by the research team to deliver the 6-week intervention consisting of an initial face-to-face CRC educational presentation using the S2S video, two weeks of phone-call follow-up, and three weeks

of text message follow-up. The intervention was delivered by the CHA to African Americans in North Florida who are patients of the participating CHCs and were not up to date with CRC screening.

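### The Cox analyses name no event-time source and no tie method; if only 3- and 12-month status is held, the hazard ratio and its significance depend on an unstated setting (minor)

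*Combined protocol and SAP*

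**What the plan says.** The primary comparison is a chi-square test on the proportions screened by 12 months (Statistical analysis). Beyond it, the same section plans Cox models over time: "baseline, 3 months, and 12 months), we will estimate hazard ratios by fitting Cox proportional models using time-varying covariates". Receipt of screening is to be "regressed at each actual time point on time elapsed since baseline to test for an interaction between time and treatment group". The proportional hazards check is described thus: "the Kaplan-Meier curve and the Schoenfeld residuals will be used for fixed and time-varying covariates, respectively". The closing paragraph of the section uses Cox, or other suitable survival models, to test treatment by moderator at each measurement time.

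The Study Protocol section describes screening only at two times. It defines the primary outcome by 12 months after the intervention, and adds: "The intermediary CRC screening outcome is measured at 3-months".

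No section defines a screening date, its source, the censoring rule or the tie method. The only described enquiry about completing the test is the advisor's calls in weeks 2 and 3, which only the intervention arm receives (Community health advisor and educational materials).

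**The concern.** A continuous-time Cox model needs to know when each event happened. If the data are screened or not screened at 3 months and again at 12 months, about half the trial's events or more share one event time and the rest share the other. The partial likelihood then depends heavily on how ties are approximated. The plan leaves that choice to whatever the program applies when nothing is specified.

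At stake are the overall hazard ratio, the time-by-treatment test and the moderator tests. The same data could be significant under one setting and not under the other, with nothing in the plan to say which result counts.

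**Working it through.** The documents give no hazard ratio, event count or screening rate, so there is no planned figure to reproduce. The check asks how much the tie method matters if only status is held.

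**Inputs from the documents.** 115 randomized 1:1; two-sided 5% level; assessments at 3 and 12 months; an effect threshold of "at least 15% higher than that in the control arm".

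**Assumptions.** Arms of 58 and 57; the threshold read as 15 percentage points; proportional hazards; control screening at 3/12 months of 15%/30% (A), 25%/35% (B) or 35%/50% (C).

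**Step 1: true hazard ratio.** HR = ln(1 − p₁)/ln(1 − p₀) at 12 months.
- A: ln 0.55/ln 0.70 = 1.68
- B: ln 0.50/ln 0.65 = 1.61
- C: ln 0.35/ln 0.50 = 1.51

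**Step 2: tied events.** The intervention rate at 3 months is 1 − (1 − p₀)^HR, which gives 23.9%, 37.0% and 47.9%. In C, events at 3 months are 58 × 0.479 + 57 × 0.35 = 27.8 + 19.95, about 48. Events by 12 months are 58 × 0.65 + 57 × 0.50 = 66.2, so about 18 more occur at 12 months. A gives 22 + 21 and B gives 36 + 13.

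**Step 3: what each tie method estimates.** The Breslow estimate θ solves Σ d₁ = Σ d·r₁θ/(r₁θ + r₀) over the two times. Here d is all events, d₁ is intervention events, and r₁ and r₀ are the numbers at risk. In C the numbers at risk are 58 and 57, then 30.2 and 37.05. At θ = 1.384 the right side is 47.75 × 0.585 + 18.45 × 0.530 = 37.7, which equals the left side, 27.8 + 9.9. Efron removes the tied events from the risk set step by step.

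| Case | True HR | Breslow HR | Efron HR |
|---|---|---|---|
| A | 1.68 | 1.58 | 1.67 |
| B | 1.61 | 1.50 | 1.60 |
| C | 1.51 | 1.38 | 1.50 |

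**Step 4: effect on the test.** 20,000 simulated trials per case, Wald tests (simulation error at most 0.4 points).

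| Case | Breslow rejects | Efron rejects | Complementary log-log rejects | Breslow and Efron differ |
|---|---|---|---|---|
| A | 28.6% | 37.4% | 38.0% | 8.8% |
| B | 24.5% | 36.5% | 37.4% | 12.0% |
| C | 20.1% | 36.7% | 37.9% | 16.6% |

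Every disagreement had Efron significant and Breslow not. With no true effect, Breslow rejects in 1.7% to 2.9% of trials and Efron in 4.5% to 4.7%. The error is conservative.

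**Step 5: a single data set.** Take 29 of 58 against 17 of 57 screened by 3 months, then 9 of 29 against 11 of 40 by 12 months. Breslow gives HR 1.48 (p = 0.116), Efron 1.64 (p = 0.048), and the complementary log-log model 1.66.

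**Step 6: where the problem fades.** With low rates (control 5%/10%) the true HR is 2.73, Breslow gives 2.61, and verdicts differ in 4.2% of trials. With tests dated to the day, the two hazard ratios agree to two decimals and verdicts differ in 0.1% to 0.3%.

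**Step 7: moderator model.** Assume a binary moderator splitting the sample in half, with no effect in one half and 30 points in the other. Breslow rejects in 22%, 20% and 18% of trials, Efron in 30%, 32% and 37%.

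**Step 8: time origin.** The Cox text counts from baseline, while the primary outcome counts from the end of an intervention lasting up to 6 weeks. If the two arms were counted differently, the first interval could be 42 days longer in one arm, on about 91 days.

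**The case against.** The strongest reply is that the harmful case is not established. Time points described as actual, elapsed time since baseline, Kaplan-Meier curves and Schoenfeld residuals all fit dated events better than two status checks. Dated clinic records are also plausible: "Both intervention and control groups received the FIT from their CHC", and "The CHCs were blinded to study arm". This stands. A reader might infer that the plan has chosen a wrong model; the documents do not support that. They show a missing definition of event time. They do not show that dates exist either.

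A second reply is that little depends on it. The primary test does not use event times, the Cox models carry no decision rule of their own, and even the better methods reach only about 37% power for a 15-point effect. This also stands, and it keeps the point minor. It does not remove it, because a setting that can decide significance should be written down.

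A third reply is that the plan already has alternatives: other survival models for moderators, and GEE for multivariate analyses. The first is true, so the remedy is within the plan there. On the second, GEE can handle binary status at two times, but the plan assigns the time-by-treatment test to Cox.

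A reader might also infer that ties could produce spurious positive findings. The null simulations show the opposite: neither method exceeds 5%.

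**Conclusion.** The omission is certain; the consequence is conditional. If only 3- and 12-month status is held, Breslow ties shrink the hazard ratio by about 0.10 to 0.13 and lose 8.8 to 16.6 points of power against Efron, under the three assumed pairs of control rates, proportional hazards and a 15-point effect. The loss is smaller at low screening rates and close to nil with dated tests. There are no excess false positives. It would be wrong to conclude that the trial's main result is in doubt, since the chi-square comparison uses no event times. Severity is minor, with medium confidence, because the documents do not settle which kind of event time is held.

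**What to change.** State the source of the event time, then follow the matching branch.

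1. **Only status is held.** Fit binary regression with a complementary log-log link on person-interval records (0-3 and 3-12 months), with arm, interval and the listed covariates. The arm coefficient of this main-effects model is the overall log hazard ratio. Fit a second, separate model with a one-degree-of-freedom arm × interval term (0-3 against 3-12) as the time-by-treatment and proportional hazards check, and report its confidence interval. With standard errors of the log ratio of 0.62, 0.65 and 0.56 in A, B and C, 80% power needs a ratio of interval hazard ratios of exp(2.80 × SE), about 5 to 6. A non-significant result is therefore not evidence of proportional hazards. For moderators, fit a model with the moderator and arm × moderator. Cox with Efron ties is an acceptable minimum.
2. **Test dates from one source exist in both arms.** Keep Cox on those dates with Efron or exact ties. Do not date events from the intervention-only advisor calls.
3. **Either way,** use one time origin in both arms, reconciling the baseline and post-intervention definitions.

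Two clarifications are optional. One is a rule for participants whose 3-month status is missing but whose 12-month status is known, given the statement "Analyses were performed using an intent-to-treat approach that includes all participants randomized". The other is to name arm and arm × time as the Cox terms, since elapsed time has no estimable main effect there.

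The cost is SAP wording and simple SAS reprogramming. Branch 1 uses only status the plan already measures. Branch 2 needs dates that the documents do not show to exist.

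### Effects over time are assigned to a Cox time-by-arm term that, after 3 months, compares only people not yet screened, so a late hazard ratio below 1 need not mean that later screening was suppressed

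*Combined protocol and SAP*

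**What the plan says.** The Study Protocol section makes screening by 12 months the primary outcome and adds an earlier one: "The intermediary CRC screening outcome is measured at 3-months". For the primary outcome the Statistical analysis section is clear: "The chi-square test was used to compare the two treatment arms for screening receipt". The analysis is intention-to-treat, in everyone randomized.

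For the effect over time (baseline, 3 and 12 months), the same section specifies Cox hazard ratios, with screening "regressed at each actual time point on time elapsed since baseline to test for an interaction between time and treatment group". The model is then repeated with adjustment for age, income, marital status, education and other significant baseline covariates. For the proportional-hazards assumption, "the Kaplan-Meier curve and the Schoenfeld residuals will be used for fixed and time-varying covariates, respectively".

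The section names a GEE procedure for multivariate work but does not tie it to an outcome or to visits. It does not spell out an arm comparison of the cumulative 3-month proportion. It does not say that a hazard ratio after 3 months is conditional on being unscreened, or how an interaction is to be interpreted.

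**The concern.** A hazard ratio for months 3 to 12 uses only people who had not been screened by month 3. The intervention runs for six weeks at most and is aimed at completing the test, so it acts before that point. If it works, it takes the more willing people out of its own risk set. Those left behind in the intervention arm are then, on average, harder to persuade than those left in the control arm. Randomization does not protect that comparison.

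The natural question for an early outcome and a later one is how much of the early lead remains at 12 months. That concerns cumulative proportions in everyone randomized. The late hazard ratio answers a different, conditional question. A value below 1 could be reported as the intervention discouraging later screening when it did no such thing and its arm is still ahead.

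**Working it through.** **Inputs from the documents.** Number randomized: "115 participants were randomized at the time of enrollment following completion of the baseline survey", allocated 1:1, hence 58 and 57. Tests are two-sided at 0.05. Everyone is not up to date with screening at entry. The intervention ends by six weeks. The documents give no control rate, hazard ratio or event count, so there is no planned figure to reproduce, and all rates below are assumptions.

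**Model.** A share s of people is reachable. A proportion e of them is screened by 3 months, and e depends on arm. Of the reachable people not yet screened, 50% are screened in months 3-12 **in both arms**. All others have a 5% chance per interval in both arms. Arm therefore has no effect on anyone after 3 months.

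- P3 = s·e + (1−s)·0.05
- P12 = P3 + s(1−e)·0.50 + (1−s)·0.95·0.05
- Early HR = ln(1−P3, intervention) / ln(1−P3, control)
- Late HR = ln[(1−P12)/(1−P3)] for intervention, divided by the same quantity for control

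**Scenario A (s = 0.5; e = 30% control, 60% intervention).**

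- Control: P3 = 0.15 + 0.025 = 0.175; P12 = 0.175 + 0.175 + 0.02375 = 0.37375.
- Intervention: P3 = 0.30 + 0.025 = 0.325; P12 = 0.325 + 0.100 + 0.02375 = 0.44875.
- Reachable share among those unscreened at 3 months: control 0.35/0.825 = 42%; intervention 0.20/0.675 = 30%. The late risk sets differ in make-up.
- Late HR = ln(0.55125/0.675) / ln(0.62625/0.825) = 0.2025/0.2756 = 0.73.

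| Scenario (s; e control v intervention) | Control, 3 / 12 months | Intervention, 3 / 12 months | Lead, 3 / 12 months (points) | HR 0-3 | HR 3-12 |
|---|---|---|---|---|---|
| A (0.5; 30% v 60%) | 17.50% / 37.38% | 32.50% / 44.88% | 15.0 / 7.5 | 2.04 | 0.73 |
| B (0.4; 30% v 70%) | 15.00% / 31.85% | 31.00% / 39.85% | 16.0 / 8.0 | 2.28 | 0.62 |
| C (0.6; 25% v 50%) | 17.00% / 41.40% | 32.00% / 48.90% | 15.0 / 7.5 | 2.07 | 0.82 |

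**Without heterogeneity.** Put s = 1. Then (1−P12)/(1−P3) = 0.50 in both arms and the late HR is exactly 1.00. The result depends on people differing in propensity.

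**Other forms of heterogeneity.** Here control rates are 20%/40% or 30%/50% at 3/12 months, and each person's early hazard is multiplied by 2 or 3 and the late hazard by 1. Gamma frailty with variance 0.5, 1 and 2 gives late HRs of 0.77-0.91, 0.66-0.85 and 0.58-0.79. If 20% never screen the late HR is 0.65-0.91; if 40% never screen it is 0.33-0.78. The intervention arm is ahead at 12 months in every case.

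**What a trial of this size would show.** Simulation with 58 intervention and 57 control participants, scenarios A, B, C; significance by Wald test on grouped complementary log-log estimates:

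- Late HR estimate below 1: 74%, 81%, 68% of trials. With no heterogeneity it is already 48-50%, by chance alone.
- Below 1 while the 12-month proportion favours intervention: 53%, 62%, 47%.
- Significantly below 1: about 6-10%. Significantly below 1 while the 12-month proportion favours intervention: about 1-3%.
- The lead at 12 months is smaller than at 3 months: 86-92%.

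**The case against.** The strongest reply is that the problem is neither inevitable nor likely to yield a false significant result. A reader might infer that any intervention that works early and then stops will look as if it suppresses later screening. The documents do not support that: with equal propensity the late hazard ratio is 1.00, and the covariate-adjusted model removes part of any heterogeneity. The listed covariates are unlikely to remove all of it, so the risk remains, but as a possibility.

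A reader might also infer that a negative time-by-arm term should never be read as waning. That goes too far. In these scenarios the lead really does shrink, and an arm-by-visit comparison of cumulative proportions would usually show the same. With no heterogeneity the interaction is significantly negative in 20-45% of simulated trials, where it correctly shows fading. Apparent suppression requires the late hazard ratio itself to be below 1.

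Two further readings are tempting. One is that arm gets no formal test of proportional hazards, only a plot. The planned time-by-arm term is itself such a test, so the gap concerns the fixed baseline covariates. The other is that listing elapsed time as a regressor spoils the model. It has one value for everyone in a risk set, so its main effect cannot be estimated, but dropping it changes no estimate.

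Finally, the general chi-square comparison of key variables between arms may be meant to cover the 3-month outcome, and nothing in the plan says a late hazard ratio will be read as harm. Both are fair, but the plan states neither the 3-month contrast nor the interpretation.

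**Conclusion.** The concern holds in a limited form. The one analysis assigned to effects over time rests, after 3 months, on groups selected after randomization, and the plan does not say so. If propensity to screen varies beyond the adjusted covariates, the late hazard ratio can fall to about 0.6-0.8 in scenarios A-C with no individual effect after 3 months and a remaining lead of about 8 points. The wider set of assumed models gives 0.33-0.91. Every rate, frailty variance and never-screener share here is assumed.

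The practical risk is a misread direction in a secondary analysis rather than a significant false finding. The primary 12-month comparison is not exposed, and the plan does not support a claim that suppression will appear.

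**What to change.** In the Statistical analysis section, define the analysis over time as the arm difference in cumulative proportion screened at 3 and at 12 months, each with a confidence interval, in all randomized participants. Fit it with the GEE procedure already named: participant as cluster, 3- and 12-month visits only (nobody has the outcome at baseline), and an arm-by-visit term. Report the two differences as well as that term, so that a shrinking lead is not mistaken for a lost one.

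Keep the Cox model as supplementary. Label any hazard ratio after 3 months as conditional on being unscreened at 3 months, and state that a value below 1 will not be read as suppression of screening.

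Two minor tidy-ups: drop elapsed time as a main effect, and apply Schoenfeld-residual tests to the fixed baseline covariates.

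The cost is SAP wording and one extra model from a planned procedure. No new data are needed. The Cox result loses some prominence.
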